4.2 Outcomes

Four outcomes are studied in step 2. Firstly, hospitalization for heart failure (ICD-9 code 428.xx, ICD-10 code I50) will be studied and secondly all-cause mortality will be assessed (only in UK (CPRD and THIN) and the Nordic countries). Read codes will be listed separately. Acute myocardial infarction (ICD 9 code 410 and ICD 10 code I21) and atrial fibrillation (ICD 9 code 427.3 and ICD 10 code I48) will be assessed descriptively.

4.3 Other Variables and Covariates

Covariates will be measured to describe baseline characteristics of the study population. A set of core covariates will be determined where data is available in all databases and is described in the full protocol (D1690R00015). Additional covariates will be described

where available in specific databases. Baseline covariates will be measured prior to the index date (including) (age will be on index date) and by clinical coding from either primary or secondary care records. Therapies at baseline will be assessed in the twelve months before and on the index date except for diabetes medication at baseline. Diabetes medication at baseline will be assessed in the twelve months before the index date (excluding).

5. STATISTICAL ANALYSIS PLAN

5.1 Statistical Methods – General Aspects

The incidence rates for heart failure hospitalization will be compared between new initiators of the SGLT-2 inhibitors and the comparison arm (new initiators of other GLD) using hazard ratios (or some other appropriate measure) and corresponding 95% confidence intervals. In this ratio, SGLT-2i as a class will be considered the test treatment. All-cause mortality will also be compared between the SGLT-2 group and control group (other GLD) using similar statistical methods. The treatment comparisons for both these endpoints will be performed separately for each individual country and the point estimates will then be pooled together for an overall weighted summary estimate using the DerSimonian-Laird meta-analysis approach [6].

5.1.1 Primary Objective(s): Calculation of Epidemiological Measure(s) of Interest (e.g. descriptive statistics, hazard ratios, incidence rates, test/retest reliability)

Propensity score

To assess the possible imbalances in baseline covariates between treatment groups which may result in confounding, a propensity score approach will be utilized. Propensity scores will be calculated after the relevant inclusion/exclusion criteria are applied. The propensity score for each subject is the predicted probability of being assigned to a particular treatment conditional on a set of observed covariates. All observed variables that may affect treatment assignment or the outcome of interest will be included in the propensity score [7]. The variables to be considered for the estimation of the propensity score include age at index date, gender, duration of lookback time, indicator variable for time from start of the study period to the index date, indicator variable for whether the index medication was an add-on or switch from the previous medication, medical conditions, cardiovascular risk factors, indicators of diabetes severity (including duration of diabetes), short or long term insulin use, other concomitant medications, lifestyle/socioeconomic status indicators, and indicators of health care utilization. Patients will be grouped into categories such that patients within a certain category should have similar propensity scores. To determine whether there is balance in key covariates between treatment groups, the covariate distribution between the treatment groups will be compared by creating a table with the frequency distribution of each key covariate by index drug use before and after propensity score matching. For matching the following method is proposed: nearest neighbor caliper width of 0.25 multiplied by the standard deviation of the propensity score distribution [7].

Descriptive analyses

Once the propensity scoring has been applied and the matched groups of SGLT-2i and control subjects have been created, certain baseline and disease characteristics (covariates) will be described by treatment group. These baseline characteristics can include age, gender, duration of diabetes, HbA1c, geographic region of residence, medical conditions, cardiovascular risk factors, concomitant medications, and certain lifestyle/ health care utilization variables, as data permit. These lifestyle/ health care utilization variables can include body mass index, smoking history, alcohol use, socioeconomic status, race/ethnicity, number of outpatient visits, number of hospitalizations, number of emergency department visits, and number of specialty care visits. These characteristics will be assessed for all patients and for patients at high baseline CV risk, respectively.

Categorical variables will be described by frequencies and percentages. Continuous and count variables will be described using mean (\pm standard deviation [SD], 95% confidence intervals (95%CI), median (quartiles), and minimum and maximum values. The proportion of patients falling above/below certain weight/BMI and HbA1c thresholds will be derived.

The incidence of acute myocardial infarction and atrial fibrillation respectively will be estimated by country/database and by treatment group.

Comparative analyses

Incidence analyses of hospitalization for heart failure and all-cause mortality will be conducted by treatment group. Only the first episode of the event will be included in the incidence analyses (however, the subsequent events within a subject will be summarized descriptively in a separate display). Person-time at risk for each patient will be the length of the index exposure episode, defined as the number of days from the day after the index prescription start date to the last day of follow-up. For each outcome of interest, the crude incidence rate in each index exposure group is the number of incident events divided by the total number of person-years at risk and will be expressed per 100 person-years with 95% confidence intervals. The incidence rates for the SGLT-2i group and control group will then be compared using a hazard ratio and corresponding 95% confidence interval. This analysis will be performed using Cox proportional hazards regression or some other suitable method if the assumptions for the Cox model are not met.

An as-treated approach will be used for the primary analysis to account for additions or switches to the index assigned treatment. A grace period of the duration of last issued prescription will be applied. As a sensitivity analysis, an intent-to-treat approach will also be applied in which subjects will be analyzed according to the treatment they were originally assigned to, regardless of whether there were any subsequent treatment changes. Further details regarding both these approaches, including the censoring rules, potentially allowing for time varying factors and imputation of missing data, will be provided in the SAP.

Meta-analysis

A meta-analysis approach, based on the DerSimonian and Laird method [6], will be used where the hazard ratio point estimates for each country are pooled together to obtain an overall summary weighted point estimate. In this approach, random-effects models with inverse variance weighting for each country will be implemented. Up to a 1:3 treatment allocation ratio of SGLT-2i to control patients will be applied to ensure that there are enough SGLT-2i patients for analysis.

5.2 Bias

5.2.1 Methods to Minimize Bias

As this is an observational study, it is important to address and minimize potential sources of bias which may affect the interpretation of study results. One such bias that may occur is channeling bias which occurs when patients with certain baseline characteristics are more likely to be prescribed a certain treatment over another treatment. Hence, this may lead to differences in baseline characteristics between the treatment groups which may confound the relationship between the treatment group and the outcome, especially if the baseline characteristics are known to be correlated with the outcome. To address this potential source of bias, propensity scoring will be used to adjust for potential covariate differences between the treatment groups. Matching the patients in the SGLT-2i and comparator groups by the propensity score should minimize the potential confounding by these covariates.

5.2.2 Adjustment for Multiple Comparisons

Not applicable.

5.2.3 Strengths and Limitations

- This study will include data from multiple countries in order to increase the power of the analyses
- Because of the real world observational data, the population of this study will be more diverse compared to a randomized controlled trial and the results of this study will be more generalizable to a broader diabetes population.
- This study will provide some insight on the potential cardiovascular benefits of SGLT-2i/dapagliflozin ahead of the DECLARE study results.
- The set of core outcomes and variables will be limited to ensure as large as possible population
- The data in selected (to be selected) databases reflects everyday health care and is collected for non-research purposes. Therefore, clinical values are captured as part of routine clinical practice and there is considerable variation in the timing and completeness of measurements
- Some databases reports issued prescriptions only. In these cases, no information may be available as to whether the patient collected the prescription and used the product. However, if a product is repeatedly issued this most likely indicates that the medication is used.
- The index prescription i.e. the first prescription of a SGLT-2i medicine may not be the first ever SGLT-2i prescription for the patient in GP based EMR databases. For example, the first prescription may have been initiated by a consultant but then the

general practitioner will usually continue the care which could be a scenario in databases like CPRD and THIN.

- Will not be possible to define the outcome exactly equivalent to EMPA-REG as the databases will most likely not have all the required tests recorded
- Comparators will likely have earlier index dates to larger extent than SGLT-2i users and thus may have longer follow up
- Combination use of several of the classes of interest or a history of use of several of the classes of interest will occur and a classification of this will be assessed
- Patients may have limited persistence with their SGLT-2i treatment
- Cannot interpret statistical analyses from this study in the same way as could be done with a randomized clinical trial because this is an observational study
- The 1:3 treatment allocation ratio of SGLT-2i:other GLD patients may reduce the representativeness of the SGLT-2i patients selected for this study compared to the overall SGLT-2i patient population

5.3 Sample Size and Power Calculations

Power calculations

The primary endpoint will be hospitalization for heart failure. A risk reduction in this endpoint of 20% for the SGLT-2i group compared to the control group will be considered clinically meaningful. For 85% power to detect a risk reduction of 20% with a two-sided alpha level of 0.05, and up to 1:3 treatment allocation of SGLT-2i to the comparator arm, a total of 970 events will be needed across both treatment groups and all databases after the matched SGLT-2i and control groups have been created (Table 1). This calculation assumes the background rate of hospitalization for heart failure in the standard of care group is 0.625 events per 100 person-years and assuming a 20% reduction a rate of 0.5 events per 100 person years in the SGLT-2i group. For 1:3 treatment allocation, approximately 40,842 person-years will be needed in the SGLT-2i group and 122,526 person-years will be needed in the control group. However, the key driver for the power and the analysis is the number of events. The sample size is merely an approximation of how many person-years might produce the required number of events based on the assumed event rates. Also, the ratio of SGLT-2i: control matching may vary across the databases but as long as a total of 970 events are achieved, the analysis will be sufficiently powered.

The background rate of 0.625 events per 100 person-years is relevant for US, UK and Germany based on literature and empirical rates from the databases included in the study. Based on Swedish data, a substantially higher rate of 1.58 events per 100 person years has been observed. This difference in rates could be due to the age distribution and other factors including case ascertainment and baseline cardiovascular risk.

As there may not be enough statistical power for a standalone analysis in any of the individual country databases, a meta-analysis approach will be used to conduct the treatment comparison by pooling the hazard ratio estimates from all of the databases assuming that a total of 970 events have been observed. The higher rate of 1.58 events per 100 person years may apply in Sweden and the other Nordic countries. This higher event rate allows for the possibility of a sufficiently powered analysis in the Nordics alone. If 970 events have been observed in the Nordics, then a separate analysis will be submitted

for the Nordics database. Assuming 1:3 matching, approximately 16,019 person-years will be needed in the SGLT-2i group and 48,054 person-years will be needed in the control group to obtain the target of 970 events.

Table 1 displays the target number of events and total exposure time (in person-years) needed for the SGLT-2i and control groups under different estimates for risk reduction, power, and SGLT-2i: control treatment allocation ratios :

Table 1. Exposure time needed for hospitalization for heart failure (person-years) if SGLT-2 rate is 0.5 events/100 patient-years.

Number of controls per SGLT-2i patient	Number of events			Total exposure time (SGLT-2i + control)			SGLT-2i exposure time		
	80	85	90	80	85	90	80	85	90
30% reduction									
1	255	290	340	42000	47765	56000	21000	23882	28000
3	340	380	460	51459	57514	69622	12865	14378	17405
5	470	545	610	69263	80316	89895	11544	13386	14982
25% reduction									
1	385	440	515	66000	75429	88286	33000	37714	44143
3	520	600	700	83200	96000	112000	20800	24000	28000
5	710	790	940	111130	123652	147130	18522	20609	24522
20% reduction									
1	635	730	850	112889	129778	151111	56444	64889	75556
3	850	970	1160	143158	163368	195368	35789	40842	48842
5	1160	1350	1520	192000	223448	251586	32000	37241	41931
15% reduction									
1	1195	1370	1600	219622	251784	294054	109811	125892	147027
3	1620	1870	2120	286130	330286	374442	71532	82571	93610
5	2220	2500	2900	387077	435897	505641	64513	72650	84274

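### 970 events give 85% power for a single common-hazard-ratio analysis at 1:3 person-time, not for the planned DerSimonian-Laird pool of seven country estimates

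*Combined protocol and SAP*

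**What the plan says.** Section 5.3 sets the target. Power and effect size are given as "For 85% power to detect a risk reduction of 20" per cent. The test is specified "with a two-sided alpha level of 0.05". On matching and size, the section says that for "up to 1:3 treatment allocation of SGLT-2i to the comparator arm, a total of 970 events will be needed". The rates behind it are that "the background rate of hospitalization for heart failure in the standard of care group is 0.625 events per 100 person-years", set against "a rate of 0.5 events per 100 person years in the SGLT-2i group". The person-years given are 40,842 and 122,526, which is exactly 1:3.

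The same section then says that the matching ratio may differ between databases, but that "as long as a total of 970 events are achieved, the analysis will be sufficiently powered". The synopsis (Sample Size Estimations) repeats this.

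The analysis is fixed elsewhere. Section 5.1 compares treatments within each country and pools the results by DerSimonian-Laird; under Meta-analysis in Section 5.1.1, "random-effects models with inverse variance weighting for each country will be implemented". Section 3.1 lists seven countries. Section 5.2.3 adds that "Comparators will likely have earlier index dates to larger extent than SGLT-2i users and thus may have longer follow up". No between-country variance of the hazard ratio is stated anywhere, and none enters Section 5.3 or its Table 1.

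**The concern.** The power calculation and the planned estimator are different things. A random-effects interval contains a between-country variance term, which an event count for a single comparison does not cover. DerSimonian-Laird also truncates its estimate of that variance at zero. Chance variation between countries therefore often yields a positive estimate when the true value is zero, and the interval can only widen in response.

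The 970-event count is the plan's stated criterion of adequate power for the pooled primary analysis. Section 2.1 judged the feasibility of Step 2 against the power calculations in Section 5.3. If true power is lower, a non-significant pooled result could be over-read as coming from a study with only a 15% chance of missing a 20% reduction.

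**Working it through.** **Inputs from the plan (Sections 5.3 and 3.1).** Hazard ratio 0.80, two-sided alpha 0.05, power 85%, SGLT-2i share of person-time 0.25, 970 events, rates 0.5 and 0.625 per 100 person-years, seven countries.

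**Assumptions, not in the documents.** Tau, the between-country standard deviation of the log hazard ratio: 0 to 0.15. Country event shares: equal, or 35/20/15/12/8/6/4%. Excess comparator follow-up: 10%, 25%, 33%.

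**1. Reproduce the plan's figure.** Schoenfeld events = (1.960 + 1.036)² / [(ln 0.80)² × 0.25 × 0.75] = 962. Power with 970 events = Φ(0.2231 × √(970 × 0.1875) − 1.960) = Φ(3.009 − 1.960) = 85.3%. Person-years check: 40,842 × 0.005 + 122,526 × 0.00625 = 204 + 766 = 970. The figure is sound for a single comparison with a common hazard ratio.

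**2. Power of the planned estimator.** Each of 200,000 replicates draws seven country log hazard ratios around ln 0.80, estimates tau² by DerSimonian-Laird, truncates it at zero, and tests the inverse-variance pooled estimate at two-sided 0.05. This was done in two ways:

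- *Variances known:* within-country variance fixed at 1/(0.1875 × country events).
- *From counts:* 970 events split over countries by a multinomial draw, SGLT-2i events drawn binomially at 1:3 person-time, and log rate ratios with estimated variances used as an approximation to Cox estimates.

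| Assumed tau | Variances known (unequal / equal shares) | From counts (unequal / equal shares) |
|---|---|---|
| 0 | 78% / 80% | 71% / 74% |
| 0.05 | 76% / 78% | 68% / 72% |
| 0.10 | 70% / 73% | 63% / 67% |
| 0.15 | 62% / 65% | 55% / 59% |

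At tau = 0 the estimated tau² is positive in about 42% of replicates (41-42% across the versions). A common-effect pool of the same data has 85.3% power with variances known and about 78% from counts, so the random-effects step costs roughly 5 to 8 points either way. The rest of the shortfall in the count version comes from few SGLT-2i events per country (204 / 7 ≈ 29) and estimated weights. A single pooled test on those counts has 83%.

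**3. Longer comparator follow-up (common effect, full 1:3 matching).** If comparators are followed f times as long on average, person-time is 1:3f and the SGLT-2i share is a = 1/(1 + 3f). Power = Φ(0.2231 × √(970 × a(1 − a)) − 1.960).

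| f | Person-time | Power with 970 events | Events for 85% |
|---|---|---|---|
| 1.00 | 1:3 | 85.3% | 962 |
| 1.10 | 1:3.3 | 83.5% | 1,011 |
| 1.25 | 1:3.75 | 81% | 1,085 |
| 1.33 | 1:4 | 79% | 1,126 |

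In the other direction, at equal follow-up 970 events give 90.6% at 1:2 and 93.5% at 1:1.

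**The case against.** The sentence can be defended as being about the matching ratio only. The plan caps matching at 1:3, and at equal mean follow-up any lower ratio raises power, so within that cap the sentence is conservative for a common-effect analysis. That stands. It is also fair that 970 is a planning threshold rather than a stopping rule, since the study period ends at the latest available data, and that neither the estimator nor its interval is wrong. If tau were known to be zero and no variance had to be estimated, power would be 85.3%. But the planned method does estimate tau², so this does not rescue the claim.

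Some stronger readings are tempting but unsupported:

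- *That 970 is an arithmetic error.* It reproduces.
- *That background rates of 0.625 and 1.58 show heterogeneous treatment effects.* Section 5.3 suggests age distribution, case ascertainment and baseline cardiovascular risk as reasons. Different baseline risk is not a different hazard ratio, so the results for tau above zero are illustrations.
- *That the 1:5 row of Table 1 (1,350 events) refutes the sentence.* The plan does not match at 1:5. The row shows only that required events depend on the ratio.
- *That comparator follow-up will be materially longer.* Section 5.2.3 gives no amount. Section 5.1.1 lists time from study start to index date among the propensity-score variables, which may reduce the imbalance. As-treated follow-up ends with index treatment, so an earlier index date need not mean proportionally longer follow-up. Matching below 1:3 would offset it.
- *That the Nordic standalone analysis is underpowered at 970 events.* The plan does not say how the three Nordic countries would be combined, and the seven-country simulation does not address it.

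**Conclusion.** The statement that 970 events suffice does not hold for the planned DerSimonian-Laird analysis. The shortfall exists without any true heterogeneity: about 71-80% power against a stated 85%. No single value in that range should be treated as the answer, because it depends on country event shares, which are assumed here, and on how within-country variances are handled. Further loss for tau above zero is conditional on heterogeneity that the documents do not quantify.

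The follow-up point is secondary and conditional. The sentence holds for matching up to 1:3 if mean follow-up is similar, and a 10% excess costs under 2 points.

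**What to change.** In Section 5.3 and the synopsis, replace the sentence with a statement that 970 events give 85% power only for a common-effect analysis with a person-time ratio no more extreme than 1:3.

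Restate the power of the planned DerSimonian-Laird analysis from a simulation that uses the Step 1 country event shares and counts. Tabulate it over assumed tau (0, 0.05, 0.10, 0.15) and realised person-time ratio. Do not write a fixed figure such as 78-80% into the plan, since it rests on assumed shares and known variances.

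State how the Nordic standalone analysis combines its countries, and apply the same qualification if it uses DerSimonian-Laird.

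The cost is one reworded sentence in two places, one simulation and one small table. No extra patients and no change of estimator are needed. The only downside is a less favourable stated power.

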6. STUDY CONDUCT AND REGULATORY DETAILS

6.1 Data Management

6.1.1 Study Flow Chart and Plan

This study will be carried out internally to the largest extent possible. We will utilize the internal AZ access to Humedica. Combining THIN and CPRD data requires the analysis to be conducted by a contractor (CEIFE). The MarketScan data are analyzed by the Truven Health analytics.

The Swedish and Danish data (DAISY and DAFFODIL) will be updated with data on hospitalization diagnoses for 2015 which will be available in Q4 2016. Norwegian data (DAPHNE) is currently waiting to be delivered, estimated to November 2016. The Nordic/Baltic MC has access to all these databases and will conduct the analyses. The German data (DPV) will be updated quarterly and the Q2 2016 data will be available September 2016.

The Canadian data will be received from The Manitoba Centre for Health Policy (MCHP), in Q4 2016 for part 1 and Q2 2017 for part 2. These data will be analyzed by researchers at the University of Manitoba and Seven Oaks Hospital, and not internally at AZ Canada.

